## 2.9 Rationale for the research project

National bodies in Europe and elsewhere differ in their guidelines on management of diabetic patients undergoing surgery and small observational studies confirm wide variability in practice and perioperative management between centers.[1-3] Whether this variability in practice affects postoperative outcome among diabetic patients in countries across Europe has not been investigated.

Further, our sub-group analysis will provide novel data on how patients with different strata (levels) of preoperative glycaemic control progress in the postoperative period. Poor preoperative glycaemic control is associated with postoperative complications in retrospective studies [10,11]. If this study confirms an association between poor preoperative glycaemic control and adverse outcomes, then the beginning of personalised perioperative medicine for diabetic patients will be enabled. For example, it is known from intensive care medicine that patients with better pre-admission glycaemic control ( $HbA1c < 53$  mmol.mol) have worse outcomes if they develop hyperglycaemia, compared with patients whose pre-existing glycaemic control was already poor ( $HbA1c > 69$  mmol.mol) [4,11]. If this pattern was reflected in the perioperative management of diabetic patients, it would enable a more personalized approach in the perioperative period. Similarly, whether our other subgroups outlined differ in postoperative outcomes is unknown.

This large, multicentre, international prospective observational study will address these urgent research questions and so create a platform for better management and outcomes for patients undergoing surgery with this high risk, highly prevalent condition, which is increasing in incidence in the European population.

## 2.10 Risk-Benefit Assessment

MOPED is a prospective cohort study of the medical management and outcome of diabetic patients during and after surgery. Therefore, risks are limited to data protection. Data protection will be guaranteed through encoding and the use of a secured database with restricted access by individual log-in and graduated user rights. Further, only pseudonymised data will be stored centrally. The database will be hosted on servers physically located in the European Union and data can only be transferred to servers located in member States of the European Union or in third countries which level of personal data protection has been

determined as adequate by the European Commission (based on General Data Protection, EU Regulation 2016/679, Article 45).

### 3. OBJECTIVES, ENDPOINTS/OUTCOMES AND OTHER STUDY VARIABLES

#### 3.1 Objectives

1. To document, in a large scale observational, epidemiological study, the perioperative glycaemic management of established diabetic patients undergoing every type of surgery with anaesthesia in Europe.
2. To document the type, incidence and severity of all postoperative complications occurring up to 30 days postoperatively.
3. To document the impact of all complications by determining the number of days at home at 30 days (DAH-30, primary outcome), Comprehensive Complications Index (CCI) score, based on the Clavien-Dindo scale and other secondary outcomes.
4. To undertake sub-group analysis comparing these outcomes among:
  - DM1, DM2 and Other Diabetes ('Other' includes Maturity Onset Diabetes of the Young, (MODY) and LADA and any other type of diabetes).
  - Patients with different strata of pre-operative glycaemic control, i.e. HbA1c <53, HbA1c 53-69 and HbA1c >69 mmol. mmol;[11]
  - Patients who received different anaesthetic techniques:
    - Volatile versus total intravenous anaesthesia.
    - Regional versus general anaesthesia (GA) and
    - Patients receiving combined GA and regional anaesthesia versus GA alone.

A list of the a priori hypotheses is listed in Appendix 9.

#### 3.2 Primary and secondary endpoint/outcome(s)

Primary endpoint: Days at Home at 30 days (DAH-30) [12,13]

Secondary endpoints:

Comprehensive Complications Index (CCI) score, based on Clavien-Dindo scale; [14,15]

Quality of Recovery scale (QoR-15), only taken from patients who are in hospital the day after surgery, i.e. Day 1 postoperatively [16], 30-day mortality,

Length of Stay in Hospital, Length of Stay in ICU if applicable.

Incidence of specific major adverse events as listed in European Perioperative Clinical Outcomes Definitions manuscript[18], (see Appendix 11 'Definitions of Outcomes') (MI, MINS, AKI, PPC, CVA, PE, DVT, AKI, Postoperative pulmonary infection (PPI));

Tertiary end-Points:

Intraoperative and postoperative management techniques of diabetes therapy will be documented, including fasting capillary/ABG blood glucose levels before, and <3hr after surgery. Also, peak blood glucose recorded during surgery, if available.

Also: incidence of diabetic ketoacidosis (defined as presence of the triad of: glucose > 12 mmol.L; ketonaemia > 3.0 mmol.L and lactaemia > 2.0 mmol.L);

Incidence and duration of use of IV Insulin Infusion Therapy.  
Incidence of hypoglycaemia (glucose < 4 mmol/l or severe < 2,5 mmol/l).

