	*Diabetics of longer duration have higher risk of intraoperative hypotension due to autonomic neuropathy.
Outcomes	
Primary endpoint: Days at Home at 30 days after surgery (DAH-30)
 
Secondary endpoints: Comprehensive Complications Index (CCI) score, Quality of Recovery (QoR-15) Day 1 if applicable, 30-day mortality, Length of Hospital Stay, Incidence of specific major adverse events (as listed exhaustively see Appendix 11 'Definitions of Outcomes')
 
Tertiary endpoints: Time to resumption of normal diabetes therapy (insulin or oral hypoglycaemics and diet), Incidence of Diabetic Ketoacidosis or Hypoglycaemia, Incidence and duration of use of IV Insulin Infusion Therapy, Change in diabetic management at 30 days
 
Intraoperative and postoperative management techniques of diabetes therapy will be documented, including capillary blood glucose levels before, during and <2hr after surgery.

Inclusion & Exclusion Criteria	
Inclusion criteria: Diabetic patients aged 18 years or over (all classes except gestational diabetes) undergoing surgery (defined as requiring any general anaesthesia technique or any specific regional anaesthetic technique or a combination). Ambulatory, elective or emergency surgery and patients who receive postoperative care in intensive care or high dependency units will be included. Pre-defined subgroups of diabetic patients will be highlighted for later analysis.
 
Exclusion criteria: Patients who are not diabetic; Patients with gestational diabetes; Patients undergoing minor surgery, i.e. surgery under local anaesthetic infiltration alone with or without monitored sedation alone or surgery not as defined in the inclusion criteria above.

Project Measurements	
Patients' consent will be requested to allow documentation of their perioperative course and 30-day outcome as outlined in the outcome measures.
 
Apart from routine clinical care, no intervention is planned.

Number of Participants	5,000
Duration	In each participating centre, recruitment of new patients will continue for a period of 12 months after their registration with ESAIC as a participating centre, until the target 5,000 patients is reached. Follow up duration to 30 days after surgery.
Centres	This will be an international, multicentre prospective observational study. Any centre where colleagues can enrol and collect the data outlined in a minimum of n=45 patients are welcome to participate.

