## 6. PROJECT ASSESSMENTS

### 6.1 Project table of procedures and assessments: Figure 1.

PIs or designees will screen the elective surgical schedule for eligible patients. This may include screening patients attending the preoperative clinic if the surgery is planned within three months. The time window between answering the consent and surgery cannot exceed 90 days. Because of the minimal interference to normal clinical care which this study proposes, patients may also be invited to participate on the day of surgery, provided they receive this request on the ward before coming to theatre.

As it will also be particularly important to include diabetic patients undergoing emergency surgery, these patients will need to be screened and give informed consent on the day of surgery or up until to hospital discharge.

Intraoperative and postoperative management techniques of diabetes therapy will be documented, including capillary blood glucose levels before, during and <2hr after surgery. Also: Time to resumption of normal diabetes therapy (insulin or oral hypoglycaemics and diet); incidence of diabetic Ketoacidosis (defined as presence of the triad of: glucose > 12 mmol.L; ketonaemia > 3.0 mmol.L and lactaemia > 2.0 mmol.L; Incidence and duration of use of IV Insulin Infusion.

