## 7.3 Planned analyses

### 7.3.1 Main analysis

The aim of this research is to describe and quantify the epidemiology of the perioperative management of diabetic patients in Europe. Descriptive statistics such as mean (SD), median [interquartiles, range] and frequencies (%) will be presented as appropriate. The precision of the estimates will be reported with 95% confidence intervals to show the prevalence and incidence rates of diabetic phenotypes and major adverse events and complications.

The primary outcome measure is Days at Home at 30 Days (DAH-30).

Secondary outcomes include: Comprehensive Complications Index (CCI) score, based on Clavien-Dindo scale and the QoR-15 instrument measuring quality of recovery, taken only in patients who remain in hospital for Day 1 postoperative.

Secondary outcomes also include 30-day mortality, length of hospital stay, incidences of specific major adverse events (MI, MINS, AKI, PPC, CVA, PE, DVT and surgical site infection (SSI).)

Univariate analyses will be used to help identify variables of potential interest for multivariable analyses, in addition to stepwise selections. Robust multivariable regressions using maximum likelihood estimation (MLE), including Poisson and negative binomial, will be used to identify significant associations. Specific factors, or subsets of interest, will be investigated further using linear mixed models with MLE. Binary and categorical outcomes, such as occurrence of a postoperative pulmonary complication (PPC) will be analysed using multivariable logistic regression, survival analysis and Cox proportional hazards regression as appropriate.

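### Three secondary and tertiary endpoint rules are faulty as written: ketoacidosis has no acid-base criterion, the two lists of named adverse events differ, and the postoperative glucose measurement is described in two ways

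*Protocol*

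**What the plan says.** **Ketoacidosis.** The Synopsis lists "Incidence of Diabetic Ketoacidosis or Hypoglycaemia" among the tertiary endpoints without defining either. Section 3.2 supplies the case definition: "defined as presence of the triad of: glucose > 12 mmol.L; ketonaemia > 3.0 mmol.L and lactaemia > 2.0 mmol.L". Section 6.1 gives the same triad, ending "ketonaemia > 3.0 mmol.L and lactaemia > 2.0 mmol.L".

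**Named major adverse events (secondary endpoints).** Section 3.2 lists "MI, MINS, AKI, PPC, CVA, PE, DVT, AKI, Postoperative pulmonary infection (PPI". Section 7.3.1 gives a list that ends "PE, DVT and surgical site infection (SSI". The Synopsis names no events and refers to Appendix 11, which is not among the pages available.

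**Perioperative glucose (tertiary).** Section 3.2 asks for fasting capillary or ABG "blood glucose levels before, and <3hr after surgery", plus the peak value during surgery where one is available. Section 6.1 asks for "capillary blood glucose levels before, during and <2hr after surgery", and the Synopsis agrees with section 6.1.

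**The concern.** The first item is a case definition that does not measure what its name says. The second and third are pairs of passages that cannot both be followed.

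Ketoacidosis is one of the few outcomes here that is specific to diabetes. If its rule admits patients without acidosis and excludes some with it, the reported incidence is that of a different condition. A later analysis plan cannot repair this unless acid-base values were collected.

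The event list decides which incidences are reported as named secondary endpoints. SSI is a notable absence from the section that defines endpoints. Section 2.8 treats diabetes as raising SSI risk in its own right, and the study cited in section 3.1 for the HbA1c strata is, by its title in the reference list, about glycated haemoglobin and sternal wound infection.

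Perioperative glycaemic control is the subject of the first research question in the Synopsis, so the time and sample for the postoperative value should be stated once.

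**Working it through.** The point rests on comparing passages. The plan states no figure to reproduce.

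**(a) Ketoacidosis triad.** Inputs: the definition in sections 3.2 and 6.1, which agree. An event requires glucose > 12 AND ketones > 3.0 AND lactate > 2.0 mmol/L. Of the three limbs, none is pH or bicarbonate and one is lactate. Two invented patients show what the rule does:

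| Patient | Glucose > 12 | Ketones > 3.0 | Lactate > 2.0 | Acidotic | Counted |
|---|---|---|---|---|---|
| A: high glucose, high ketones, lactate 1.5 | yes | yes | no | yes | no |
| B: 12.1 / 3.1 / 2.1, normal pH | yes | yes | yes | no | yes |

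Both errors follow from the wording alone. Their frequency depends on how lactate and pH are distributed among ketotic surgical patients, and the protocol gives nothing on that.

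**(b) Event lists.**

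- Section 3.2: MI, MINS, AKI, PPC, CVA, PE, DVT, AKI again, PPI. Nine entries, eight distinct.
- Section 7.3.1: MI, MINS, AKI, PPC, CVA, PE, DVT, SSI. Eight entries, all distinct.
- In both: MI, MINS, AKI, PPC, CVA, PE, DVT, which is seven.
- In section 3.2 only: PPI. In section 7.3.1 only: SSI.
- Either list: 7 + 1 + 1 = 9 distinct events, so two of nine depend on which section is followed.

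**(c) Glucose.**

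| Feature | Section 3.2 | Section 6.1 and Synopsis |
|---|---|---|
| Postoperative window | under 3 h | under 2 h |
| Sample | capillary or ABG | capillary |
| During surgery | recorded peak, if available | level during surgery |

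The windows are nested: any value taken before 2 h satisfies both. They disagree only for a value taken from 2 h up to 3 h, which is valid in section 3.2 and out of window elsewhere. The share of patients in that interval is not known.

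**The case against.** The best defence is that the operative documents lie elsewhere. Appendix 11 is named as the full source of outcome definitions, and section 6.3 applies it. Section 6.4 sends the reader to the eCRF for details. Sections 8.1 and 8.2 describe one English-language eCRF with common SOPs and training. PPI may be meant as part of PPC, which is in both lists, and the second AKI looks like a slip. The two statements of the ketoacidosis triad agree, so that item is a choice of definition and not a conflict. All the outcomes concerned are secondary or tertiary.

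Much of this limits the point without removing it. A complete appendix or a single-window form would settle practice, but the protocol would still give two lists and two windows. Agreement between sections 3.2 and 6.1 does not supply the missing acidosis criterion.

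Several stronger readings are tempting, and the documents do not support them:

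- *Untested patients count as non-cases.* No passage says so. Section 7.3.3 speaks of analysing observed data, and coding of untested patients would sit in the CRF and its guidelines, which are not shown.
- *Incidence is understated by some stated share.* Neither the frequency of ketoacidosis nor the lactate distribution is given, so any such figure would be an assumption restated.
- *SSI or pulmonary infection would go unrecorded.* Section 3.1 sets out to document every complication to day 30, and section 6.2 bases the complications index on chart review and patient questioning. What is unclear is which of the two is a named endpoint.
- *Centres will differ because they follow different sections.* With a common eCRF this is possible but not shown.
- *Every patient's glucose value is affected.* The nesting of the windows rules this out.

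**Conclusion.** The point holds for three specifications. As worded, the ketoacidosis rule can misclassify in both directions, by an amount that cannot be derived from the documents. The named secondary events differ between sections 3.2 and 7.3.1 by two of nine. The glucose passages differ in window, sample type and intraoperative measure, and the window matters only for values taken between 2 and 3 hours.

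The conclusion about ketoacidosis assumes only that an endpoint carrying that name is meant to identify acidosis. The other two conclusions need no assumption beyond the text. Neither the primary endpoint, DAH-30, nor the sample size of 5,000 is affected. The changes are worth making, but the main result does not depend on them.

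**What to change.** 1. **Ketoacidosis.** In sections 3.2 and 6.1, replace the lactate limb with an acid-base criterion (pH or bicarbonate) taken from a published definition that the steering committee chooses. Use charted values where available. Report the number of patients who had the needed tests alongside the incidence.
2. **Event list.** Use one list of named major adverse events in sections 3.2 and 7.3.1, consistent with Appendix 11. Include SSI, enter AKI once, and state whether PPI is separate from PPC.
3. **Glucose.** Reconcile section 3.2 with section 6.1 and the Synopsis on window, sample type and intraoperative measure, and carry the agreed version into the CRF completion guidelines. The documents do not show which version was intended.

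The cost is wording in the Synopsis and sections 3.2, 6.1 and 7.3.1, and perhaps one or two eCRF fields if the form does not already hold acid-base values. The real downside is in item 1. The study adds no tests to routine care, and the protocol mentions ABG only as an alternative source for glucose. Patients without a charted pH or bicarbonate will therefore be unclassifiable, which is why the tested number must be reported.

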## 4. PROJECT DESIGN

### 4.1 Type of research and general project design

MOPED is a prospective, observational, international, multicentre cohort study.

### 4.2 Study centres and role of national and local PIs

Any hospital in Europe (as defined by the World Health Organisation) is welcome to participate as a study centre. Non-European centres may be accepted upon request to the SC. Centres will be asked to enrol a minimum of 45 patients (up to 200) over a recruitment period of up to 18 months from the date of the centre's registration with ESAIC. No more than one quarter (25%) of a centre's patients can be day cases (ambulatory anaesthesia). Study centre registration occurs online via the dedicated "Call for Centres form" on the ESAIC website. Within the overall Europe-wide period of recruitment planned for MOPED (at least 18 months), the start of recruitment for individual centres is soon as possible after centre registration with ESAIC, provided that there is prior IRB approval. Recruitment will continue until enrolment of the planned sample size (n=5,000).

National coordinating investigators are anaesthesiologists appointed by ESAIC and the SC to lead the project within individual countries and their responsibility includes:

- Identify centres in their country and recruit local PIs in participating hospitals;
- Assist in the translation of required study documents;
- Ensure that all necessary national or regional regulatory approvals are in place prior to start of patient inclusion;
- Assist and train the Local PI and monitor the conduct of the study according to ICH-GCP;
- Ensure good communication with ESAIC headquarters and the participating sites in his/her countries during all study steps including data cleaning.

Local PI may be anesthesiologists, surgeons or diabetes physicians working in perioperative medicine in each participating institution who will have the following responsibilities:

- Provide leadership for the study in their institution;
- Ensure all relevant regulatory/ethical approvals are in place for their institution;
- Ensure adequate training of all relevant staff prior to data collection;
- Supervise enrolment, daily data collection, and assist with problem solving;
- Adjudicate events
- Ensure timely completion of eCRF, follow-up assessments, and data cleaning queries. The Local PI is the main person responsible for ensuring integrity of data collection. By signing the data on eCRF Local PI confirms the data integrity;
- Communicate with ESAIC headquarters and the relevant National Coordinating Investigator during all study steps including data cleaning.

Maintain and update their investigator's site file according to the recommendation of the ICH-GCP Guidelines E6(R2).

### 4.3 Procedures

At screening day ("day -90" to "day of surgery", i.e. within 3 months of planned day of surgery), patients will be screened and be asked for consent (see 2.4). (see Appendix 2 'Patient Information Sheet' and Appendix 3 'Patient Consent Form'). For emergency surgery, diabetic patients' consent may be requested on the ward, immediately prior to coming to theatre on the day of surgery and up until hospital discharge.

If patients remain in hospital on the day of surgery, some data will be documented on the first day postoperatively (“Postop Day 1”), including QoR-15 quality of recovery score, taking 3-5 minutes.

Some patient data will also be recorded on Day of Discharge, provided the patient is discharged within 30 days of their surgery.

At Day 30 after surgery, data will be collected by telephone if the patient has been discharged. If still in hospital, patient data will be collected on the ward on Day 30.

There is some flexibility with the timing of data collection. Example: If Day of Discharge or follow-up Day 30 falls on a weekend, follow up may be conducted the next available working day. Similarly, if the patient cannot be contacted on Day 30, the patient should be contacted the next available day, e.g. Day 31. In this case, all outcomes recorded should be those that occurred up to and including Day 30 after surgery.

Table 1: Summary table of the timings of assessments

When	Action/Parameters Collected
Day-90 to Day 0	Screening Inclusion/Exclusion criteria Consent if elective Patient and diabetes baseline data Screening failure tracking SORT score
Day 0	Emergency patient screening and consent* Diabetes and patient baseline data if not already Surgical parameters SORT score Anaesthetic and PACU parameters
Day 1 Post-Op	QoR-15 Glucose and insulin parameters over 24 hr since surgery
Day of Discharge	Postoperative morbidity / complications CCI score
Day 30 Post-Op	DAH-30 (primary outcome) Mortality Postoperative morbidity / complications CCI score Length of Stay Diabetes parameters post surgery

\*Consent can be taken from patients undergoing emergency surgery up until the day of hospital discharge

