#### 2.4 Participant Information and Informed Consent

Written, informed consent, using the approved Informed Consent Form (ICF), will be sought from each patient prior to inclusion unless an explicit, written exemption by the responsible IRB is provided. Patient Information Leaflet (PIL) and any other written information to be provided to the patients as well as advertisement for subject recruitment (if used) must be subject to IRB review and given approval/ favourable opinion.

If applicable, patients' consent will be sought as follows: Prior to surgery, the patients will be presented with the IRB-approved PIL providing information for participant to make an informed decision about their participation in the study, i.e. explaining the nature of the study, its purpose, the general lack of any procedures involved, the expected duration, the potential risks and benefits and any discomfort participation may entail. (see Appendix 2 Patient Information Sheet, Appendix 3 Patient Informed Consent Form).

Each participant will be informed that their participation in the study is voluntary and that he/she may withdraw from the study at any time and without explanation, that withdrawal of consent will not affect his/her subsequent medical assistance and treatment and that no further data will be collected, while already collected, encoded data will be pseudonymised and analysis may be performed up to the point of data collection.

The participant will be informed that his/her medical records will be examined by authorised individuals other than their treating physician. The participant will read the statement and will have the opportunity to ask questions before signing and dating the ICF, and will be given a copy of the signed document. Patients will confirm that they were given adequate time to reach a decision. The ICF must also be signed and dated by the investigator (or designee) and it will be retained as part of study records.

Diabetic patients listed for both elective and emergency surgery will be approached by a member of the research team and invited to participate.

While for elective patients, consent may be obtained in a preoperative clinic up to 90 days prior, for emergency surgery diabetic patients' consent may be requested on the ward, immediately prior to coming to theatre on the day of surgery and up until hospital discharge.

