#### 4.4 Recruitment and Screening

The PI or designee will screen the surgical schedule for eligible patients. This may include screening patients attending the preoperative clinic if the surgery is planned within three months. Because of the minimal interference to normal clinical care which this study

proposes, patients may also be invited to participate on the day of surgery, provided they receive this request on the ward before coming to theatre.

This is justified because there is even less knowledge currently about the management and outcomes of diabetic patients undergoing *emergency* surgery, who are acknowledged to be a particularly high-risk group, than diabetic patients undergoing elective surgery. Therefore, including a cohort of emergency surgery diabetic patients is particularly important to evaluate risk factors for adverse outcomes which may be mitigated. There is also anecdotal evidence that practice of managing these patients varies widely between nations and individual centres. The Surgical Outcome Risk Tool (SORT) will be used to indicate surgical risk [17]

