#### 4.5 Methods of minimising bias

In every centre, all diabetic patients undergoing surgery, (except where there is only conscious sedation, with or without local anaesthetic infiltration or topical anaesthesia to the eye) are eligible. Centres are invited to enrol their target number of patients (depending on number of investigators in their team) from the date of registration of their centre with ESAIC and all approvals being in place, for up to 12 months. No other exclusion criteria apply, even emergency surgery patients are eligible. Therefore, we do not believe that significant risk of bias exists.

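### Emergency patients may be consented up to discharge, so entry can depend on survival, capacity and stay; Section 4.5's conclusion of no significant bias does not follow

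*Protocol*

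**What the plan says.** **Consent window for emergency patients.** Section 2.4 says that their "consent may be requested on the ward, immediately prior to coming to theatre on the day of surgery and up until hospital discharge". The footnote to Table 1 in Section 4.3 repeats it: "Consent can be taken from patients undergoing emergency surgery up until the day of hospital discharge". Section 6.1 extends the window to screening: "these patients will need to be screened and give informed consent on the day of surgery or up until to hospital discharge".

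**A different rule in Section 4.4.** Patients may be invited on the day of surgery, "provided they receive this request on the ward before coming to theatre". The next paragraph justifies this by the need to include emergency patients.

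**Consent as the condition of entry.** Under Section 2.4 written consent "will be sought from each patient prior to inclusion unless an explicit, written exemption by the responsible IRB is provided". For centres without an exemption, no route is given for a patient who dies or is discharged before being approached.

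**Time zero.** DAH-30, mortality, complications and length of stay run from surgery to Day 30 (Sections 3.2 and 4.3).

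**The statement on bias.** Section 4.5 says that every diabetic surgical patient is eligible apart from the sedation, local and topical cases, and that nothing further excludes anyone. It concludes: "Therefore, we do not believe that significant risk of bias exists". The same section has centres enrol a target number; consecutive enrolment is not stated. Sections 4.2 and 9.1 cap day cases at 25% of a centre's patients, although Section 5.1 admits ambulatory surgery without limit.

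**Existing safeguard.** Section 6.4 asks each centre, at the end of the study, for a count of eligible patients, a count of screening failures, and the reasons for failure.

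**The concern.** In a cohort whose outcomes start at surgery, membership should be settled at or before surgery. Here, an emergency patient can be brought in after part of the outcome has already happened. Two selection mechanisms follow:

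- Patients who die, or remain unable to consent, before anyone approaches them are missed.
- Patients discharged quickly are also missed, and those who stay longer have more chances to be approached.

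Both act on quantities that make up the endpoints. DAH-30 is the primary outcome, and 30-day mortality and length of stay are secondary. Sections 2.4 and 4.4 single out emergency patients as a high-risk group about whom little is known, so their estimates matter to the study's purpose. Centres may also apply different consent rules (before theatre under 4.4, up to discharge under 2.4, or none under an exemption). That could create apparent differences between centres in a study that asks whether practice varies between centres and nations.

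The day-case cap and the target numbers are a separate and milder matter. They shape the case mix behind any pooled figure.

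**Working it through.** The plan gives no figure on this point, so there is none to reproduce. The check has two parts.

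**1. The passages side by side**

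- Sections 2.4, 4.3 and 6.1 agree that emergency consent may come after theatre. Section 4.4 requires the invitation before theatre and gives emergency patients as its reason. The before-theatre condition also appears in 6.1, but there it sits in the paragraph on the elective schedule and emergency patients are treated separately. Section 4.4 makes no such separation.
- Section 4.5 goes from who is eligible to a conclusion about bias. Bias depends on which eligible patients are enrolled. The section mentions neither the late window nor the cap, and it does not ask for consecutive enrolment.
- The forms in 6.4 count and explain non-inclusion. The example reasons are refusal, language and cognitive difficulty. Table 1 places screening-failure tracking in the Day -90 to Day 0 row and does not list it in the row for emergency screening. A patient who dies before being screened may therefore never be logged.

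**2. Illustrations of size**

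Every input below is an assumption; the protocol supplies none.

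(a) *Deaths before consent.* Let m be true 30-day mortality in emergency patients and f the share of those deaths that occur before consent. Patients consented before theatre contribute nothing to f. Observed mortality = m(1 − f)/(1 − mf). For m = 5% and f = 25%: 0.0375/0.9875 = 3.8%.

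| True m | f = 10% | f = 25% | f = 50% |
|---|---|---|---|
| 2% | 1.8% | 1.5% | 1.0% |
| 5% | 4.5% | 3.8% | 2.6% |
| 10% | 9.1% | 7.7% | 5.3% |

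Taken alone, this mechanism lowers observed mortality by about 9% to 50% in relative terms.

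(b) *Stay-dependent approach.* Let h be the daily chance rate of being approached and L the stay in days. Probability of entry = 1 − exp(−hL). Take half the patients with L = 2 (DAH-30 of 28) and half with L = 10 (DAH-30 of 20), so the true mean is 24.0.

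| h | Entry, L = 2 | Entry, L = 10 | Ratio | Enrolled mean DAH-30 |
|---|---|---|---|---|
| 0.1 | 0.181 | 0.632 | 3.5 | 21.8 |
| 0.2 | 0.330 | 0.865 | 2.6 | 22.2 |
| 0.5 | 0.632 | 0.993 | 1.6 | 23.1 |

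(c) *Day-case cap.* Let s be the true day-case share, with mean DAH-30 of 29 in day cases and I in inpatients. The cap changes the pooled mean by −(s − 0.25)(29 − I) when s exceeds 0.25. For I = 24 and I = 20 the falls are 0.75 and 1.35 days at s = 40%, 1.25 and 2.25 at 50%, and 1.75 and 3.15 at 60%. At s of 25% or less the cap has no effect.

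Mechanism (a) makes outcomes look better; (b) and (c) make DAH-30 look worse. The protocol does not allow them to be netted.

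**The case against.** The strongest reply is that the late window is an option and also does good. Table 1 puts emergency screening and consent on Day 0; later consent is only permitted. Patients who are sedated, ventilated or otherwise without capacity just after surgery can enter only if the window stays open, and Section 5.1 expressly includes intensive-care patients. This stands. A reader might infer that the remedy is an early enrolment deadline, but that would remove the sickest patients who later regain capacity, and it would not recover early deaths or early discharges.

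Centres with a consent exemption need not have the problem. This also stands, though it adds a difference between centres.

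A reader might infer that emergency mortality will be understated. The documents do not support that as fact: longer stayers are over-represented and may have higher mortality, so the net sign is open. A reader might also infer that an emergency-versus-elective comparison is compromised. The subgroup comparisons listed in Sections 3.1 and 7.3.4 are diabetes type, HbA1c stratum and anaesthetic technique, and the appendix of prior hypotheses is not shown.

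The cap is a disclosed enrolment quota and not an eligibility criterion, so it does not strictly contradict the statement that nothing further excludes patients. It affects the representativeness of pooled figures more than comparisons within a stratum.

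Finally, the consent form is dated, and the case report form, the screening form and the analysis plan are not shown; some of what is needed may already be there. That limits what can be called missing. It does not rescue the argument in 4.5, and the end-of-study counts in 6.4 do not by themselves correct any estimate.

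**Conclusion.** The point holds as a flaw in how enrolment is fixed and in what Section 4.5 concludes from it. For non-exempt centres that use the late window, entry of emergency patients can depend on survival, capacity and length of stay, all of which bear on DAH-30, 30-day mortality and length of stay. Section 4.4 conflicts with 2.4, 4.3 and 6.1 on when such patients may be asked. Section 4.5 reaches its conclusion from eligibility alone and leaves out the late window, the target numbers without a consecutive-enrolment rule, and the 25% cap.

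Neither size nor net direction can be derived from the protocol. The illustrations rest wholly on assumed inputs and show only that each mechanism could matter. How much it matters depends on how many emergency patients are consented late, which the study can learn only if it records it. A bias of unknown sign is a reason to measure and report it, and no ground for saying that it is absent.

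**What to change.** 1. Reconcile Section 4.4 with 2.4, 4.3 and 6.1, so that one rule on the timing of emergency consent applies throughout.
2. Keep the late window, but record the date and time of consent relative to surgery in the eCRF, or confirm that it is already there.
3. Log every eligible emergency patient from the time of surgery on the existing Screening Failure form, with death before approach and discharge before approach as separate reasons.
4. Add two sensitivity analyses: mortality with delayed entry at consent, and DAH-30 restricted to patients consented before surgery or treated in exempt centres. The analyses may sit in the analysis plan, but the data for them must be captured during recruitment. Delayed entry addresses deaths before consent; it does not by itself remove selection on capacity or early discharge, which is why the log is also needed.
5. Report outcomes by emergency/elective and by day-case/inpatient, and split the eligible counts on the End of Study form in the same way.
6. Replace the last sentence of Section 4.5 with a statement of these selection risks, including the target numbers and the effect of the cap where day cases exceed 25%.

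Cost: a short amendment, one eCRF field, extra columns on two existing forms, and some further analysis. The restricted analysis will have fewer patients. Those it keeps were well enough to consent before theatre or come from exempt centres, so it supplements the main analysis and does not replace it.
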